Positive hepatitis B surface antigen (HBsAg) or hepatitis C serology (regardless of treatment status) or positive hepatitis B core antibody (HBcAb) (tested at Week 44 of Study GA30044 or later, prior to entry into Study GA30066) are exclusionary.

- Patients who developed a malignancy (with the exception of non-serious local and resectable basal or squamous cell carcinoma of the skin) during the Phase II Study GA30044
- 12-lead ECG at the Week 48 visit of Study GA30044 that demonstrates clinically relevant abnormalities that may affect patient safety or interpretation of study results, including the following:
 - QTcF > 440 msec demonstrated by at least two ECGs > 30 minutes apart
- Current treatment with medications that are well known to prolong the QT interval at doses that have a clinically meaningful effect on QT, as determined by the investigator
 - The investigator may contact the Sponsor for confirmation if needed. The investigator may reference the CredibleMeds® Web site: <https://www.crediblemeds.org/pdftemp/pdf/CompositeList.pdf>.
- Estimated glomerular-filtration rate (based on the 4-variable Modification of Diet in Renal Disease equation) < 30 mL/min or on chronic renal replacement therapy
- Laboratory values from the Week 44 visit of Study GA30044 (which may be repeated once at a later unscheduled visit, if necessary) that meet the following criteria:
 - AST or ALT > 1.5 × ULN (unless due to known autoimmune hepatitis)
 - Total bilirubin > 1.2 ULN
 - Amylase or lipase > 2 × ULN
 - Hemoglobin < 7 g/dL
 - ANC < 1.5 × 10⁹/L
 - Absolute lymphocyte count (ALC) < 0.5 × 10⁹/L
 - Platelet count < 50,000/μL

End of Study

The end of this study is defined as the date when the last patient, last visit occurs. The end of the study is expected to occur 56 weeks after the last patient is enrolled.

Length of Study

The maximum time in the study for a patient is 56 weeks, including treatment for 48 weeks and an 8-week safety follow-up period after the last dose of GDC-0853. The total length of the study, from enrollment of the first patient to the end of the study, is expected to be approximately 3.5 years.

Investigational Medicinal Products

Test Product (Investigational Drug)

The investigational medicinal product (IMP) for this study is GDC-0853 50-mg tablets.

Non-Investigational Medicinal Products

Corticosteroids

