1.3.2.6 Hepatotoxicity

Evidence of hepatobiliary injury was observed in animals administered relatively high doses of GDC-0853 in repeat-dose toxicity studies. In the SAD study, the MAD study for 14 days in healthy subjects, and a study of hematologic malignancies with daily dosing for over 1 year in patients, there have been no adverse events of liver enzyme elevations or trends towards elevations in laboratory evaluations. In Study GA29350, there have been 2 cases of Grade 3 elevations in AST and ALT levels in RA patients on methotrexate, out of a total of 172 patients (as of data cutoff: 10 May 2017), but as the study is still blinded, association with GDC-0853 cannot yet be determined. For inclusion in this study, AST and ALT levels should be no more than 1.5 times the upper limit of normal (ULN), and total bilirubin levels should be normal at screening (see Section 4.1.1). Baseline and routine evaluations of AST/ALT and total bilirubin levels will be performed throughout the study. Elevated AST or ALT levels of Grade ≥ 3 ($> 5 \times$ ULN) or cases of potential drug-induced liver injury that include an elevated ALT or AST level in combination with either an elevated bilirubin level or clinical jaundice, as defined by Hy's Law (see Section 5.3.5.6), are AESIs with expedited reporting requirements to the Sponsor (see Section 5.4.2).

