4.1.1 Inclusion Criteria

Patients must meet the following criteria for study entry:

- Signed Informed Consent Form (see Section 4.4.1)
- Age 18–76 years, inclusive, at time of signing Informed Consent Form
- Able to comply with the study protocol, in the investigator's judgment
- Completion of Study GA30044 up to 48 weeks
- Acceptable safety and tolerability during Study GA30044 as determined by the investigator
- Women of childbearing potential must have a negative urine pregnancy test at baseline

A serum pregnancy test is needed on Day 1 only if the urine pregnancy test is positive.

- For women of childbearing potential (including those who have had a tubal ligation): Agreement to remain abstinent (refrain from heterosexual intercourse) or use a contraceptive method with a failure rate of < 1% per year during the treatment period and for at least 60 days after the last dose of study drug.

A woman is considered to be of childbearing potential if she is postmenarcheal, has not reached a postmenopausal state (≥ 12 continuous months of amenorrhea with no identified cause other than menopause), and has not undergone surgical sterilization (removal of ovaries and/or uterus).

Examples of contraceptive methods with a failure rate of < 1% per year include bilateral tubal ligation, male sterilization, established proper use of hormonal contraceptives that inhibit ovulation, hormone-releasing intrauterine devices, and copper intrauterine devices. Women using estrogen-containing hormonal contraceptives as a method of contraception must also use a barrier, such as a male condom, in conjunction with the hormonal contraceptives.

The reliability of sexual abstinence should be evaluated in relation to the duration of the clinical trial and the preferred and usual lifestyle of the patient. Periodic abstinence (e.g., calendar, ovulation, symptothermal, or postovulation methods) and withdrawal are not acceptable methods of contraception.

- For men: agreement to remain abstinent (refrain from heterosexual intercourse) or use contraceptive measures, and agreement to refrain from donating sperm, as defined below (also see [Appendix 5](#))

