4.1.2 Exclusion Criteria

Patients who meet any of the following criteria will be excluded from study entry:

- Met protocol-defined treatment-stopping criteria during Study GA30044
- An adverse event in Study GA30044 that required permanent discontinuation of study drug
- During Study GA30044, treatment with any therapy that is prohibited in this study (see Section [4.3.2](#))
- In the opinion of the investigator, any new (since initially enrolling in the Phase II Study GA30044), significant, uncontrolled comorbidity or new clinical manifestation (related to SLE or not) that 1) requires medications not allowed in this protocol (see Section [4.3.2](#)) or 2) could put the patient at undue risk from a safety perspective

If the Principal Investigator has questions related to exclusion, he or she should consult the Medical Monitor.

- Pregnant or breastfeeding, or intending to become pregnant during the study or within 60 days after the last dose of study drug
- Any uncontrolled or clinically significant laboratory abnormality that would affect safety, interpretation of study data, or the patient's participation in the study in the opinion of the investigator in consultation with the Medical Monitor
- Any major episode of infection requiring hospitalization or treatment with IV antibiotics within the last 4 weeks of Study GA30044
- Evidence of active, latent, or inadequately treated infection with *Mycobacterium tuberculosis* (TB) as defined as follows:
 - A positive QuantiFERON[®]-TB Gold (QFT) or T-SPOT[®] TB test or a Mantoux purified protein derivative (PPD) skin test (performed per Centers for Disease

Control and Prevention [CDC] guidelines using 5 tuberculin units per 0.1 mL) result of ≥ 5 mm of induration, performed at the Week 44 visit of Study GA30044 or later, prior to entry into Study GA30066

- Patients with a history of bacillus Calmette-Guérin vaccination should be screened using the QFT test only.
- A positive QFT test should be considered a positive diagnostic TB test.
- If initial QFT is indeterminate, perform a confirmatory test with either QFT or T-SPOT. The Principal Investigator may consult with the Medical Monitor to discuss selection of confirmatory test based on the patient's disease status and baseline immunosuppression.
- An indeterminate QFT test followed by a negative QFT or negative T-SPOT test should be considered a negative diagnostic TB test.

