- An indeterminate QFT test followed by an indeterminate QFT test or borderline or positive T-SPOT test should be considered a positive diagnostic TB test.
- Patients who experienced a de novo or reactivated serious viral infection, such as hepatitis B virus or hepatitis C virus (HCV) during Study GA30044
 - Positive hepatitis B surface antigen (HBsAg) or hepatitis C serology (regardless of treatment status) or positive hepatitis B core antibody (HBcAb) (tested at Week 44 of Study GA30044 or later, prior to entry into Study GA30066) are exclusionary.
- Patients who developed a malignancy (with the exception of non-serious local and resectable basal or squamous cell carcinoma of the skin) during the Phase II Study GA30044
- 12-lead ECG at the Week 48 visit of Study GA30044 that demonstrates clinically relevant abnormalities that may affect patient safety or interpretation of study results, including the following:
 - QTcF > 440 msec demonstrated by at least two ECGs > 30 minutes apart
- Current treatment with medications that are well known to prolong the QT interval at doses that have a clinically meaningful effect on QT, as determined by the investigator
 - The investigator may contact the Sponsor for confirmation if needed. The investigator may reference the CredibleMeds[®] Web site:
<https://www.crediblemeds.org/pdftemp/pdf/CompositeList.pdf>.
- Estimated glomerular-filtration rate (based on the 4-variable Modification of Diet in Renal Disease equation) < 30 mL/min or on chronic renal replacement therapy
- Laboratory values from the Week 44 visit of Study GA30044 (which may be repeated once at a later unscheduled visit, if necessary) that meet the following criteria:
 - AST or ALT $> 1.5 \times$ ULN (unless due to known autoimmune hepatitis)
 - Total bilirubin > 1.2 ULN

- Amylase or lipase $> 2 \times \text{ULN}$
- Hemoglobin $< 7 \text{ g/dL}$
- ANC $< 1.5 \times 10^9/\text{L}$
- Absolute lymphocyte count (ALC) $< 0.5 \times 10^9/\text{L}$
- Platelet count $< 50,000/\mu\text{L}$

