4.2.2 Dosage, Administration, and Compliance

4.2.2.1 GDC-0853 Dose and Administration

The GDC-0853 dose regimen is oral 200 mg BID. Patients will receive GDC-0853 approximately every 12 hours for approximately 48 weeks. The first open-label dose of GDC-0853 should be the a.m. dose (taken in clinic) during the Week 48 visit of the GA30044 study (which is Day 1 of Study GA30066). Patients should be directed to take one dose (a total of 4 tablets) BID (total of 8 tablets each day). On clinic visit days when PK assessments are performed (Day 1 and Week 24), patients should be instructed that GDC-0853 will be administered in the clinic.

In general, a dosing window of ± 2 hours is acceptable. If a dose is taken more than 2 hours late or is missed altogether, the patient should resume normal dosing with the next scheduled dose. Patients should record on the bottle the dose that was missed and notify study staff of any missed doses. Doses that are vomited will be considered missed doses.

A dose reduction of GDC-0853 for specific safety events is permitted (see [Table 3](#)). For a potential dose reduction for other adverse events not listed in the table, please consult the Medical Monitor. If dose reduction is indicated, the dose of GDC-0853 may be reduced from 200 mg BID to 200 mg QD or lower (in consultation with the Medical Monitor). If the adverse event resolves and the patient has increased lupus disease activity, it is up to the discretion of the investigator in consultation with the Medical Monitor to decide if the patient can resume the 200 mg BID dosing.

Guidelines for dose reduction and treatment interruption or discontinuation are provided in Section 5.1.2.

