5.1.1.6 Hepatotoxicity

Evidence of hepatobiliary injury was observed in animals administered relatively high doses of GDC-0853 in repeat-dose toxicity studies (see Section [1.3.1](#) for related primary nonclinical toxicity findings).

In clinical studies to date, including single dosing and multiple dosing for 14 days in healthy subjects and daily dosing for up to 2 years in patients with hematological malignancies, there have been no adverse events of liver enzyme elevations or trends towards elevations in laboratory evaluations.

As a safety risk-mitigation measure, to be eligible for the blinded study GA30044, AST and/or ALT levels should be no more than 1.5 times the ULN and total bilirubin levels should be $\leq 1.2 \times \text{ULN}$ at the Week 44 visit or later (prior to entry into Study GA30066). Safety monitoring for potential hepatotoxicity includes baseline and routine evaluations of AST/ALT and total bilirubin levels throughout the study as outlined in the schedule of activities (see [Appendix 1](#)).

Laboratory results of Grade ≥ 3 ($> 5 \times \text{ULN}$) AST or ALT elevation, or ALT or AST elevations $> 3 \times \text{ULN}$ in combination with clinical jaundice (total bilirubin $> 2 \times \text{ULN}$) are considered AESIs and should be reported to the Sponsor in an expedited manner as outlined in Section 5.2.3.

Guidelines for the management of study treatment in the event of hepatotoxicity in patients are provided in Table 3.

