
Hepatotoxicity
 
Any AST or ALT $> 3.0\text{--}5.0 \times \text{ULN}$
 
AST or ALT elevation $> 3 \times \text{ULN}$ in combination with total bilirubin $> 2 \times \text{ULN}$, of which at least 35% is direct bilirubin, or clinical jaundice
 
Any AST or ALT $> 5 \times \text{ULN}$
	
Withhold GDC-0853 and consult with the Medical Monitor.
 
Discontinue GDC-0853 and consult with the Medical Monitor. Recheck liver laboratory tests, including AST/ALT, ALP, and total bilirubin, and CBC with differential (to determine eosinophil count), within 1 week (preferably within 72 hours). Assess patient for signs/symptoms of hepatic failure and for other causes of liver dysfunction (e.g. viral hepatitis, concomitant medications, etc.). Continue to monitor liver function tests until abnormalities resolve. Report Hy's Law cases as AESI to the Sponsor in an expedited manner.
 
Discontinue GDC-0853 and consult with the Medical Monitor. Recheck liver laboratory tests, including AST/ALT, ALP, and total bilirubin, and CBC with differential (to determine eosinophil count), within 1 week (preferably within 72 hours). Assess patient for signs/symptoms of hepatic failure and for other causes of liver dysfunction (e.g., viral hepatitis, concomitant medications). Continue to monitor liver function tests until abnormalities resolve. Elevations of AST or ALT of $> 5 \times \text{ULN}$ should be reported as AESIs to the Sponsor in an expedited manner.

Cardiovascular effects
 
Sustained (at least two ECG measurements > 30 minutes apart) QTcF that is > 500 msec and/or > 60 msec longer than the baseline value
	
Unless there is a clear alternative cause other than study drug, discontinue GDC-0853. ^e

Table 3 Guidelines for Management of GDC-0853 in Patients Who Experience Specific Adverse Events (cont.)

Event	Action to Be Taken a
Sustained absolute QTcF that is > 515 msec	Unless there is a clear alternative cause other than study drug, discontinue GDC-0853. ^e
An episode of torsades de pointes or a new ECG finding of clinical concern	Discontinue GDC-0853. ^e
Vascular Inflammation	
Vasculitis	Consult with the Medical Monitor.

AESI = adverse event of special interest; BID = twice a day; PLT = platelet count; QD = once a day; QTcF = QT interval corrected using Fridericia's formula; SLE = systemic lupus erythematosus; ULN = upper limit of normal.

- ^a Any patient who discontinues GDC-0853 should enter safety follow-up if possible.

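### The autoimmune-hepatitis exception to the AST/ALT entry limit has no ceiling, so a patient can pass the numeric criterion at a value that meets the literal words of Table 3's withhold row

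*Combined protocol and SAP*

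**What the plan says.** **Entry.** The laboratory criteria in Section 4.1.2 use the GA30044 Week 44 sample, which may be repeated once. A patient is excluded for AST or ALT above 1.5 × "ULN (unless due to known autoimmune hepatitis"). The synopsis carries the same exception. Neither place gives exempt patients an upper limit. Total bilirubin has its own limit of 1.2 × ULN, with no exception.

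**First dose.** Section 4.2.2.1 states: "The first open-label dose of GDC-0853 should be the a.m. dose (taken in clinic"), at the GA30044 Week 48 visit, which is Day 1 of this study. Section 4.4.7 sends chemistry samples to a central laboratory. I found no requirement that a Day 1 AST/ALT result be available before dosing.

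**On treatment.** For any AST or ALT above 3.0 and up to 5.0 × ULN, the action in Table 3 is: "Withhold GDC-0853 and consult with the Medical Monitor". Above 5 × ULN, Table 3 and Section 4.5.1 call for discontinuation.

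**Judgement-based checks.** Section 4.1.1 requires: "Acceptable safety and tolerability during Study GA30044 as determined by the investigator". Section 4.1.2 also excludes: "Any uncontrolled or clinically significant laboratory abnormality that would affect safety, interpretation of study data", as judged by the investigator with the Medical Monitor.

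**Summaries elsewhere.** Section 1.3.2.6 says: "For inclusion in this study, AST and ALT levels should be no more than 1.5 times the upper limit of normal (ULN"). Section 5.1.1.6 also gives 1.5 × ULN: "ALT levels should be no more than 1.5 times the ULN and total bilirubin levels should be" within 1.2 × ULN. Neither repeats the exception.

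**The concern.** An entry limit and a hold threshold for the same test should fit together, so that nobody qualifies at a value at which the protocol would withhold the drug. For most patients they do. For patients with known autoimmune hepatitis they do not, because the exception removes the entry limit and puts no other in its place.

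At stake is the first open-label dose in a patient whose transaminases already lie in the hold range. Hepatotoxicity is a named potential risk of GDC-0853 (Sections 1.3.2.6 and 5.1.1.6). GA30044 has a placebo arm (Section 1.3), so for a patient from that arm Day 1 would be the first exposure to the drug. Without a stated value, sites may handle the same patient differently.

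**Working it through.** The plan gives no figure to reproduce. The check compares thresholds.

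**Inputs**
- Entry limit: 1.5 × ULN; no limit if the elevation is due to known autoimmune hepatitis (Section 4.1.2, synopsis).
- Hold range: above 3.0 and up to 5.0 × ULN (Table 3).
- Discontinuation: above 5 × ULN (Table 3, Section 4.5.1).
- Maximum enrolment: about 240 (Section 6.1).
- Illustrative value, my assumption: a stable 3.5 × ULN with bilirubin no higher than 1.2 × ULN.

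**Step 1: patient without the exception.** The highest admissible value is 1.5 × ULN. The rise needed to reach the hold threshold is 3.0/1.5 − 1 = 100%. The entry and hold ranges do not overlap.

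**Step 2: patient with the exception.** No value is inadmissible on AST/ALT alone, so the whole band above 3.0 and up to 5.0 × ULN is open. At 3.5 × ULN the value is 3.5/1.5 = 2.33 times the general entry limit and 3.5/3.0 = 1.17 times the hold threshold. The bilirubin limit does not cap AST/ALT.

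**Step 3: timing.** Week 44 to Week 48 is 4 weeks (28 days). A stable value that passes at Week 44 is still in the hold range when the Day 1 dose is taken.

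**Step 4: does the Table 3 row apply to a stable known value?** The row's wording takes in any AST or ALT in the range. Other rows are narrower: the lymphocyte and platelet rows include a treatment-emergent qualifier, and the neutrophil and platelet rows allow resumption at baseline. Section 5.3.5.6 likewise limits Hy's Law reporting to treatment-emergent elevations. The hold row has no such qualifier, so its literal trigger is met. If it is instead confined to adverse events, a stable value in the band has no numeric rule on transaminases alone until it exceeds 5 × ULN.

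**Step 5: how many patients.** The documents give no count. One patient would be 1/240 = 0.42% of maximum enrolment; that is a unit, not an estimate. I assume that GA30044 did not itself stop such a patient. If it stopped drug above 3 × ULN, the number is zero, because Section 4.1.2 excludes anyone who met GA30044 stopping criteria. If it only held drug at that level, that exclusion does not apply and the number is unknown.

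**Step 6: effect of a cap at 3 × ULN.** No one qualifies above the hold threshold. A patient admitted at 2.9 × ULN would reach the threshold after a rise of 3.0/2.9 − 1 = 3.4%.

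**The case against.** The strongest objection is that no affected patient may exist. Everyone entering has completed GA30044 to Week 48, and the inclusion and exclusion criteria already screen on safety during that study. Whether a patient at 3 to 5 × ULN could have stayed on drug that long depends on GA30044's own rules. This stands, and it limits the size of the point.

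Second, Section 5.1.2 presents Table 3 as guidelines for patients who experience specific adverse events and says that they do not cover every scenario. Section 5.3.5.8 counts a condition present at GA30044 screening as an adverse event only if it worsens. A stable known elevation could therefore be read as outside the table. That reading is open, but it leaves the patient without a numeric hold, so it moves the gap and does not close it.

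Third, judgement provides a route: the two checks in Section 4.1, consultation under Table 3, and resumption with approval under Section 4.5.1. These can prevent or resolve a case, but none sets a value.

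A reader might also infer more than the text supports:
- **That the protocol has two conflicting entry rules.** It does not. Sections 1.3.2.6 and 5.1.1.6 are abbreviated summaries worded as what levels should be. Section 1.3.2.6 points to the eligibility section and paraphrases the bilirubin limit loosely as normal. Section 5.1.1.6 opens by naming eligibility for GA30044 while describing values taken before entry to GA30066. Section 4.1.2 is the operative list.
- **That patients will be dosed in breach of the protocol.** The documents show only that the numeric criterion permits entry at such a value.
- **That adverse-event recording is contradictory.** Section 5.3.5.4 reports a laboratory result that changes study treatment, but also records only the diagnosis where the value is a sign of a disease. At most there is some ambiguity.

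**Conclusion.** The point holds as a minor mismatch in safety thresholds. The written AST/ALT criterion admits patients with known autoimmune hepatitis at values above 3.0 and up to 5.0 × ULN, and those values meet the literal words of the withhold row on Day 1. The checks that might intervene rest on judgement and state no number.

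The conclusion rests on the absence of any ceiling in Section 4.1.2 and the synopsis, and of any baseline qualifier in the hold row. Practical impact also requires that GA30044 did not remove such patients, which cannot be checked here; the number affected may be zero. Nothing is claimed for values above 5 × ULN, where GA30044's stopping criteria might already exclude the patient, or for other laboratory or ECG criteria. No formal test is affected. The change is optional and suits the next amendment.

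**What to change.** In Section 4.1.2 and the synopsis, write the criterion as: *AST or ALT > 1.5 × ULN (or > 3 × ULN if due to known autoimmune hepatitis)*. This keeps the exception up to the protocol's own hold threshold and leaves Table 3 unchanged.

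The alternative is a baseline-relative rule in Table 3 for these patients. It is workable, since other rows already refer to baseline, but it would allow dosing to continue above 3 × ULN and would need a new hold value that the protocol does not supply. The cap is simpler.

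As housekeeping only, have Sections 1.3.2.6 and 5.1.1.6 refer to Section 4.1.2 instead of restating the limit. In doing so, correct the eligibility cross-reference in 1.3.2.6, which points to 4.1.1, and the study name in 5.1.1.6.

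The cost is one phrase in two places and a cross-reference in two more. No tests or visits are added, because the Week 44 values are already used. The downside is that a very small number of autoimmune-hepatitis patients become ineligible. A patient admitted just below 3 × ULN may still cross the threshold later, which is what the hold is there to catch.
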